### **6.7.2 Safety Variables**

The physician will be asked to document SAEs and Adverse Events of Special Interest (AESI) on eCRFs (Section 7.0).

SAEs and Adverse Events of Special Interest (AESI) will be reported to AbbVie from the time the physician obtains the patient's authorization to use and disclose information (or the patient's informed consent/patient authorization) throughout the registry or Direct to HCP follow-up process until satisfactory conclusion or until 70 days following last dose of registry drug (whichever is longer). In the event Humira therapy is interrupted, SAEs and Adverse Events of Special Interest (AESI) will be collected throughout the interruption. If a patient switches from MTX to Humira treatment, SAEs and AEs of Special Interest will continue to be collected under the Humira arm. If treatment with Humira or MTX is permanently discontinued for any reason, patients will be discontinued from treatment and the reason for discontinuation will be recorded on the Study Drug Completion eCRF. Patients that discontinue treatment will be encouraged to remain in the registry and will be followed for safety and effectiveness through Year 5 and SAEs and AESI will be followed until satisfactory conclusion or until 70 days following last dose of registry drug (whichever is longer), and starting at Year 6, patients will be followed annually for the subset of AESI which include congestive heart failure and malignancies and SAEs through Year 10 of the registry until satisfactory conclusion or until 70 days following last dose of registry drug (whichever is longer). For polyarticular

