### **10.3.4 Analysis of Patients with Treatment Interruption (TI)**

The following summaries will be performed for patients with a treatment interruption (TI) in Humira injections. The SAEs and AEs of Special Interest collected through the HCP process will not be included in these summaries.

For the first group of safety summaries, all patients will be categorized into 2 groups: patients who have at least one TI and patients who have no TI. Two summaries of SAEs

and Adverse Events of Special Interest will compare descriptively patients who have at least one TI and patients who have no TIs:

Crude incidence: The number and percent of patients experiencing SAEs or Adverse Events of Special Interest will be tabulated for each SOC and PT.

Events per 100 patient years of observation: The number of SAEs and Adverse Events of Special Interest per 100 patient years of observation will be tabulated for each SOC and PT.

For the second group of safety summaries the longest TI will be considered and adverse event rates (SAE and Adverse Events of Special Interest) during the last on-drug period prior to the TI (i.e., the pre-TI period) will be compared to adverse event rates during the first on drug period following the TI (i.e., the post-TI period).

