**Table 2. Definition of Pre-TI and Post-TI Periods**

	Pre-TI Period	Post-TI Period
Start	First injection of the registry	Day of first injection following the longest TI
End	70 days following the last injection before the longest TI	70 days following registry completion/stop of participation

The preceding summaries do not distinguish between the same adverse events experienced by the same patients pre-TI and post-TI from the same adverse events experienced by different patients pre-TI and post-TI. Therefore, a third summary will evaluate the proportions of patients who report onset of the same adverse event pre-TI and post-TI, patients who report onset only pre-TI, patients who report onset only post-TI, and patients who do not report the event in either period.

For each TI experienced by 1% of patients and for each SAE and Adverse Event of Special Interest, the number and percent of patients who have the event or not before the TI and after the TI will be summarized as shown in [Table 3](#). This assessment will provide information about whether same or different patients experience the adverse pre-TI and post-TI.

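### Table 2 does not match the on-drug periods that Section 10.3.4 compares: its pre-TI window can span earlier interruptions, and its post-TI window can span later interruptions and time after Humira has stopped

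*Supplement*

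**What the plan says.** The second group of safety summaries in protocol Section 10.3.4 takes each patient's longest TI. It sets SAE and AESI rates in the last on-drug period before it against "adverse event rates during the first on drug period following the TI (i.e., the post-TI period"). Table 2 then supplies the dates:

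- Pre-TI: starts at "First injection of the registry" and ends "70 days following the last injection before the longest TI".
- Post-TI: starts on "Day of first injection following the longest TI" and ends "70 days following registry completion/stop of participation".

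A third summary, laid out in Table 3, is specified thus: "For each TI experienced by 1% of patients and for each SAE and Adverse Event of Special Interest". Table 2 gives windows for the longest TI only. Events from the HCP process are left out of all these summaries.

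Three other places bear on the point.

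- Section 10.1 defines a TI as more than 70 consecutive days without an injection, beginning on day 71. It notes that a patient may have several, and it removes from the Intermittent Treatment Population anyone who does not restart within a year of the last injection.
- Section 6.7.2 keeps patients under observation after the drug is stopped: "Patients that discontinue treatment will be encouraged to remain in the registry and will be followed for safety and effectiveness through Year 5". Section 6.5 encourages ten years of observation whatever the treatment.
- Sections 10.3, 10.3.2 and 10.3.3 close the treatment-emergent summaries 70 days after the last dose and exclude events during a TI.

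**The concern.** The text describes two single on-drug periods on either side of one gap. Table 2 describes two longer spans, and neither is limited to one on-drug period. A programmer cannot follow both.

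The post-TI end date depends on when the patient leaves the registry and not on any injection. Because patients stay under observation after stopping Humira, the post-TI rate can mix on-drug and off-drug time. Section 10.3.4 has no exclusion of the kind that the treatment-emergent summaries carry. The pre-TI side has a smaller fault of the same type, because its start reaches back past any earlier, shorter TI.

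At stake is the plan's direct before-and-after look at safety around an interruption, which serves the secondary objective in Section 5.0 on the impact of interruptions. Under Table 2 as written, the post/pre ratio would partly reflect how long patients remain in the registry after stopping.

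**Working it through.** Section 10.3.4 states no figure to reproduce, so the check compares the definitions and then sizes the gap on an assumed timeline.

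**Definitions side by side**

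| | Text of 10.3.4 | Table 2 |
|---|---|---|
| Pre-TI start | Start of the last on-drug period before the longest TI | First registry injection |
| Pre-TI end | End of that on-drug period | Last injection before the longest TI + 70 days |
| Post-TI start | Start of the first on-drug period after it | First injection after the longest TI |
| Post-TI end | End of that on-drug period | Registry exit + 70 days |

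The pre-TI start and the post-TI end disagree. The other two boundaries are compatible.

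**Assumed timeline (not from the documents).** Last injection before the longest TI on day 730, restart on day 980, final injection on day 1345.

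- Dosing-based post-TI window: 1345 + 70 − 980 + 1 = 436 days.
- Table 2 post-TI window: exit day + 70 − 980 + 1.
- Off-drug share f = (Table 2 window − 436) / Table 2 window.

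**Effect on the ratio.** Let ρ be the off-drug rate divided by the on-drug rate. Assume that the on-drug rate is the same before and after the TI and that the pre-TI window is wholly on drug. Then the apparent post/pre ratio = (1 − f) + f × ρ. The documents give no ρ, so a range is shown.

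| Registry exit | Table 2 window (days) | Off-drug days | f | ρ = 0.5 | ρ = 0.75 | ρ = 1 | ρ = 1.25 |
|---|---|---|---|---|---|---|---|
| Day 1710 (365 days after final injection) | 801 | 365 | 0.46 | 0.77 | 0.89 | 1.00 | 1.11 |
| Day 1826 (Year 5) | 917 | 481 | 0.52 | 0.74 | 0.87 | 1.00 | 1.13 |
| Day 3652 (Year 10) | 2743 | 2307 | 0.84 | 0.58 | 0.79 | 1.00 | 1.21 |

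A patient dosed without a gap until exit has f = 0 and no distortion.

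**Later TI.** Suppose instead that day 1345 is followed by another injection on day 1545. By Section 10.1 the TI runs from day 1416 to day 1544, which is 129 days. It is shorter than the first TI (day 801 to day 979, 179 days), so the first remains the longest. The first on-drug period of the text closes on day 1415, but Table 2 counts the 129 TI days as post-TI.

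**How long the final off-drug stretch can be.** This depends on the one-year rule in Section 10.1.

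- If it also removes patients who restart and later stop for good, the stretch is about one year at most (the first row).
- If it covers only the TI under study, the stretch can run to years (the third row: 2307 / 365.25 = 6.3 years).
- If the final gap itself counts as a TI, it would be the longest one in all three rows (at least 1710 − 1416 + 1 = 295 days against 179), and the patient would have no post-TI period.

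Later, shorter TIs are counted on any reading that leaves a post-TI period.

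**The case against.** The strongest reply is that this is a wording slip in a descriptive, secondary summary. No hypothesis test is attached, and the summaries in Sections 10.3.1 to 10.3.3 do not use Table 2. On a broad reading of the one-year rule, most of the off-drug time disappears. Interruptions can enter both windows, so the fault is partly symmetrical. These points limit the size and importance of the problem, and all of them stand. They do not reconcile the table with the text, and the final off-drug stretch still enters the post-TI side only.

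Four stronger readings are tempting, and the documents do not support them.

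- A reader might take the 4.8 and 2.8 events per 100 patient-years in Section 10.6 as on-drug and off-drug rates and infer a definite downward bias. Both are Humira serious-infection rates: 2.8 was seen in Study DE038, and 4.8 is the rate to be detected. Neither is an off-drug rate, and Section 10.3.4 covers all SAEs and AESI.
- A reader might infer that years of off-drug time are certain to be counted. That holds only on the narrow reading of the one-year rule.
- A reader might blame Table 2 for hiding a cluster of events soon after restart. Averaging over a long window would do that even if every day were on drug.
- A reader might treat this comparison as the plan's main test of restarting. The plan attaches no test to it and does not rank it so.

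On the shift table, it is fair to say that its pre-TI and post-TI terms already point to Table 2. Its wording nevertheless refers to each TI, for which Table 2 has no windows.

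**Conclusion.** The contradiction is real and has to be resolved before the summary is programmed. As written, Table 2 admits earlier TIs to the pre-TI window, and later TIs and post-discontinuation time to the post-TI window.

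Neither the direction nor the size of the effect is established. Over the assumed range (f from 0.46 to 0.84, ρ from 0.5 to 1.25), an unchanged on-drug rate would show as a ratio anywhere from 0.58 to 1.21, with no distortion at ρ = 1 or for patients dosed until exit. These figures describe single timelines. The pooled effect depends on how many patients restart and later stop, which the documents do not give. The formula also assumes even ascertainment, whereas Section 6.6.5 narrows AESI collection in Years 6 to 10 for all but the youngest group.

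The consequence is confined to the TI safety summaries.

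**What to change.** Rewrite Table 2 so that both windows follow the text of Section 10.3.4 and the plan's own treatment-emergent convention:

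- Pre-TI: from the first injection of the last on-drug period before the longest TI to 70 days after the last injection of that period.
- Post-TI: from the first injection after the longest TI to the earlier of 70 days after the last injection of that on-drug period and the last registry contact.

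Use person-time from the same windows as the denominator. Define last registry contact without the HCP process, since HCP events are excluded here while the last-contact definition in Section 10.3.1 includes it. Apply the same windows to the Table 3 shift summary, and amend its reference to each TI accordingly. State whether the one-year rule in Section 10.1 applies to any gap or only to the TI under study, and whether a final gap counts as a TI. A separate line for the first 70 days after restart is optional.

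The cost is one table and a few sentences. Dosing dates are already collected through Year 10 (Section 6.6.11), and no treatment rule changes. The price is less person-time in both windows, and so less precise rates in this summary.

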**Table 3. Sample Shift Table for Adverse Events**

Adverse Event	Adverse Event Post-TI	
Pre-TI	Yes	No
Yes	N (%)	N (%)
No	N (%)	N (%)

Additionally, summaries of the same patient's safety information before and after TI will be provided.

### **10.3.5 Analysis of Laboratory Values, Vital Signs, Tanner Maturation Staging**

Laboratory values and vital signs, when available, will be summarized by visit; shift tables will be presented for ANA and Tanner Staging showing the change from appropriate baseline.

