### **6.6.1 Demographics**

The physician will obtain patient demographic information at the enrollment visit and record it on the Baseline eCRF. The demographic information will include date of birth,

sex, race, and ethnicity (according to local regulations). Demographic data will not be captured for patients rolling over from a previous Humira (adalimumab) study as this information has already been collected. Only the patient number from the previous clinical study will be recorded in the eCRF required.

Parental heights will be requested from the biological parents, upon consent, which will be used in the analysis of the patient's growth assessment.

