### **6.6.3 Vitals, Growth Assessments and Tanner Staging**

Vitals including blood pressure, pulse, temperature, will be recorded at Baseline and at each visit through Year 5. Growth assessments, including height and weight, will be recorded at Baseline and at each visit through Year 5 and Tanner Maturation Staging ([Appendix H](#)) will be recorded at Baseline and every 12 months thereafter through Year 5. Biological parent's height will also be collected at the Baseline Visit if consent was obtained.

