**Figure 3. Treatment Period and Treatment Interruption (TI) Period**

## 10.2 Demographics and Registry Enrollment Characteristics

Baseline characteristics: age, sex, race/ethnicity, weight, height, duration of JIA, JIA disease activity and onset type of JIA Disease onset, Rheumatoid factor (RF+, RF-), HLA-B27, body mass index (BMI), prior therapies for JIA, concomitant polyarticular JIA medications, and Humira dosage and exposure duration.

Demographics and baseline characteristics will be summarized for the All Treated Patient Population. Descriptive statistics for demographics, effectiveness, and safety parameters will be presented. Number of patients with non missing values, mean, and standard deviation will be provided for continuous variables. Counts and percentages will be provided for categorical variables. The number and percentage of patients who discontinue from the registry will be summarized, overall and by reason for discontinuation. Duration of observation in the registry, registry exposure duration and total exposure duration will be summarized as follows:

Duration of observation period = the last date of registry participation (inclusive of HCP process) – enrollment date to MTX or Humira in the registry + 1

Registry exposure duration:

(MTX arm) = last MTX dose date in the registry or the first Humira dose date in the registry whichever is earlier – first MTX dose date in the registry + 1 (The first MTX dose in the registry will be on or after the enrollment date).

(Humira arm) = last Humira dose date in the registry – first Humira dose date in the registry + 14 days – total days of any treatment interruptions (The first Humira dose in the registry will be on or after the enrollment date).

Total exposure duration:

(MTX arm) = last MTX dose in the registry or the first Humira dose date in the registry whichever is earlier – first recorded MTX dose (initial dose) + 1.

(Humira arm) = last Humira dose date in the registry – first recorded Humira dose (initial dose) + 14 – total days of any treatment interruptions. For patients who rolled over from Study DE038 and were in the Placebo arm during the double-blind period of this study, the duration of the double-blind period will be subtracted from total exposure.

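### Tanner stage is analysed only as shifts from baseline without regard to age or sex, and Section 10 as shown specifies no post-baseline growth analysis although Section 6.6.1 promises one using parental heights

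*Supplement*

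**What the plan says.** **Collection.** Section 6.6.3 provides that "Growth assessments, including height and weight, will be recorded at Baseline and at each visit through Year 5". Tanner stage is recorded at baseline and every 12 months through Year 5. On parents, the same section says "Biological parent's height will also be collected at the Baseline Visit if consent was obtained", and Section 6.6.1 gives the purpose: "Parental heights will be requested from the biological parents, upon consent, which will be used in the analysis of the patient's growth assessment".

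**Analysis.** Section 10.3.5 is a single sentence. Its operative part is "Laboratory values and vital signs, when available, will be summarized by visit; shift tables will be presented for ANA and Tanner Staging", and the shifts are taken from an unspecified appropriate baseline. It names neither height nor weight, and gives no age band, sex split or arm split.

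Elsewhere in Section 10, height and weight appear only in the list in Section 10.2 that begins "Baseline characteristics: age, sex, race/ethnicity, weight, height, duration of JIA", which also includes BMI. Section 10.2 adds a general rule, "Descriptive statistics for demographics, effectiveness, and safety parameters will be presented", meaning n, mean and SD for continuous variables and counts and percentages for categorical ones.

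**The concern.** Tanner stage advances with age in healthy children. A shift table from baseline therefore fills with upward shifts whether or not treatment or disease has any effect. Delayed puberty would appear as too few shifts for the age and sex of the children concerned, and the planned table carries neither variable. Appendix H itself identifies departure from the usual sequence and tempo of puberty as the informative sign.

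The second part is an internal mismatch. Section 6.6.1 commits to using parental heights in a growth analysis, but the analysis section shown contains no growth analysis after baseline.

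The primary objective is long-term safety in children, with MTX patients as a reference group (Section 5.0). Families supply up to 5 years of growth and puberty measurements, and parents are asked for their own heights. Unless the analysis refers to age and sex, these data cannot answer the question for which they appear to be collected. Age mix may also differ between arms by design: patients who switch from MTX restart follow-up in the Humira arm (Section 6.5), and so enter it older than they entered the MTX arm.

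**Working it through.** The plan states no figure on this point, so there is none to reproduce. The check has three steps.

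**1. How far age alone drives a Tanner shift in girls**

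Inputs:
- Thelarche occurs between 9 and 13 years in 95% of girls (Appendix H).
- Staging runs for 5 years (Section 6.6.3).
- Assumption: age at thelarche is normal, with mean (9 + 13)/2 = 11 and SD = (13 − 9)/(2 × 1.96) = 1.02 years.

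For a girl at stage 1 who enters at age a, with F the distribution function of onset age:

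P(leaves stage 1 within 5 years) = [F(a + 5) − F(a)] / [1 − F(a)]

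| Entry age | P(shift), mean 11 |
|---|---|
| 4 | 0.025 |
| 5 | 0.164 |
| 6 | 0.500 |
| 7 | 0.836 |
| 8 | 0.975 |
| 9 | 0.998 |

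Appendix H also gives an average onset of puberty in girls of 10.1 to 10.5 years. With either end as the mean and the same SD, the results are 0.14 to 0.07 at entry age 4, 0.81 to 0.69 at age 6, and above 0.99 at age 8. The curve moves by less than a year and keeps its shape.

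In this model, a delay of one year is indistinguishable from entry one year younger. A girl entering at 7 with mean onset delayed to 12 has P = 0.50, the same as a girl entering at 6 with no delay. A table without age cannot tell the two apart.

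**2. Sex**

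Appendix H puts the average onset of puberty in boys at 12.2 years and gives no spread. With an assumed SD of 1.02, a prepubertal boy entering at 6 has P = 0.12 of starting puberty within 5 years. For SDs of 0.8 and 1.5 the values are 0.07 and 0.21. The girl of the same age has 0.50. The onset signs differ between the sexes, so this comparison is only indicative, but it shows that the sex mix also moves the table.

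**3. Growth: the sections side by side**

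| Item | Collected | Stated use | Analysis in Section 10 as shown |
|---|---|---|---|
| Height, weight | Baseline and each visit through Year 5 (6.6.3) | Growth assessment (6.6.3) | Baseline characteristic only (10.2) |
| Parental height | Baseline, where consented (6.6.1, 6.6.3) | Growth analysis (6.6.1) | None named |
| Tanner stage | Baseline and yearly through Year 5 (6.6.3) | Maturation staging (6.6.3) | Shift from baseline (10.3.5) |

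Appendix H shows why a growth analysis needs an age reference. Before puberty it gives 4 to 6 cm per year, and 4 × 5 = 20 to 6 × 5 = 30 cm over the 5 years of collection is normal growth.

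**The case against.** **The SAP is not shown.** Reference charts, standardised scores and table layout are commonly left to it. Section 10.4.1.4 refers to an SAP for details, although that pointer concerns the analyses in that subsection and not Section 10.3.5. This objection stands for growth: a reader might infer that parental heights are never used, but Section 6.6.1 commits to their use and the method may be in the SAP. It answers the Tanner point less well, because the protocol itself chooses the shift table.

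**Height and weight are not in Section 10.3.5.** A reader might infer that they are to be summarised as raw values by visit, from the general rule in Section 10.2 and the Table 1 row that holds vital signs and growth together. The text does not say so. Section 6.6.3 keeps the two apart: "Vitals including blood pressure, pulse, temperature, will be recorded at Baseline and at each visit through Year 5" is one item and growth assessments are another. Only the absence of a stated post-baseline analysis can be asserted.

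**Not every child shifts.** It would be too broad to say that these measures rise in every patient. Adolescents already at stage 5 cannot shift up, growth may be complete in older entrants, and by the calculation above few girls entering at 4 leave stage 1 within 5 years. This supports the point, since the rate depends on entry age.

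**A shift table conditions on starting stage.** It does, and the Appendix H forms are separate for boys and girls, so a split by sex may follow in practice. But girls of 4 and 8 at stage 1 share a row while their expected rates are 2.5% and 97.5%.

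**Growth is not prominent.** It is not named in the objectives, the AESI list or the four safety summaries, and no formal between-arm growth comparison is planned. This stands, and keeps the point at low priority.

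**Conclusion.** The point holds in two limited parts.

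- The only stated Tanner analysis ignores age and sex. It mainly reflects normal maturation and the mix of entrants, and cannot show delayed puberty. Expected 5-year shift rates for healthy girls at stage 1 run from about 2.5% to 97.5% between entry ages 4 and 8. These figures rest on the Appendix H ages and an assumed normal distribution; the ordering does not depend on the exact mean.
- Section 10 as shown specifies no post-baseline growth analysis, although Section 6.6.1 promises one that uses parental heights. This concerns the protocol text only, and the SAP may supply it.

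The documents give no basis for sizing any growth deficit, and none is claimed. The primary analysis of SAEs and AESI is unaffected. This is a desirable improvement, not a flaw that threatens the registry's main results.

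**What to change.** In Section 10.3.5, or by an explicit pointer there to the SAP:

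- Tabulate Tanner stage, and shifts from baseline, by age band and sex within each arm.
- Analyse height, weight and BMI as age- and sex-standardised scores from a named reference chart, with change from baseline at each visit through Year 5.
- As a supplementary summary, give height relative to mid-parental target height in patients whose parents' heights were provided with consent, and report how many those are.

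**Cost.** No new data are needed. Date of birth, sex, height, weight and consented parental heights are already collected; for patients from earlier studies, demographics must be linked from those studies (Section 6.6.1). The work is derivation and programming, plus choosing a reference chart suited to the United States, Europe and Australia. Age bands will leave some cells small. The mid-parental summary covers a self-selected subset and should be labelled so.
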